9.6 N/A

## **10.0 Data and Specimen Banking\***

10.1 N/A

10.2 N/A

10.3 N/A

## **11.0 Data Management\* and Confidentiality**

11.1 FSDT

Due to the ordinal nature of the FSDT data, a non-parametric repeated-measures analysis will be performed to analyze the data. Therefore, a Wilcoxon signed-rank test will be performed. For the sEMG data, a repeated measures t-test or appropriate nonparametric twin via the Wilcoxon signed-rank test if assumptions are not met for parametric analysis will be used. Descriptive statistics will be provided for the demographic data.

### **sEMG**

Data processing: Raw sEMG signals will be bandpass filtered between 10-500 Hz. The signal will be rectified, then smoothed using the Root Mean Square method with a 50ms window. The signal will be normalized to the MVIC obtained during the MVIC testing.

Data analysis: Following MVIC normalization, the mean EMG activation and peak EMG activation for each trial will be recorded. Each step-down repetition will be analyzed as a separate trial, and an average taken of all 5 trials to provide the data for each muscle pre- and post-test.

11.2 G\*power (Heinrich-Heine-University Düsseldorf, Düsseldorf, Germany) software was used to perform an a priori power analysis to determine the required N for this investigation. Data was obtained from [name] and [name] (2020), which showed a significant within-groups difference pre-exertion and five minutes post-exertion change on the FSDT ( $r = .27$ ). Pearson's coefficient was converted to Cohen's d ( $d = .56$ ). An N of 29 was calculated to achieve significant results, with beta = .80 and alpha = .05 for a two-tailed hypothesis from a repeated-measures design within groups analysis. We

assumed an attrition rate of 20% given the repeated-measures design of the investigation. Therefore, a final N of 35 will be recruited for the successful completion of this study.

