## 20.0 Resources Available

- 20.1 The two student investigators (CH and MS) are DPT students in the SAHP at LSUHS. They will be educated on the procedures of the FSDT, described in Park *et al*, sEMG electrode placement, and data collection and interpretation by the primary investigator (DF), who is a board-certified orthopedic physical therapist with 10 years of experience and the co-investigator (EM), who is a board-certified orthopedic physical therapist with 5 years of experience. The primary (DF) and co-investigator (EM) will assist the student investigators as needed throughout the study, including assisting with data collection and analysis.
- 20.2 The total number of first and second year DPT students enrolled in the SAHP at LSUHS is 67. Given the required N=35, there are enough potential participants to successfully complete this investigation. The student investigators (CH and MS) are enrolled in an independent study for the Fall 2022 semester to receive IRB approval. In the spring of 2023, the data collection portion of the study will begin and be concluded by May 2023. The investigators will be enrolled in Research IV during this semester to allow time to begin working on the poster presentation. Drs. [name] and [name] will each provide 5% FTE for their involvement in the study. During the summer semester of 2023, the student investigators will begin analyzing the data and disseminating. All data analysis will be concluded by August 2023. The motion analysis lab, room 2-217 in SAHP at LSUHS has a treatment mat, sEMG materials and technology, in addition a large open space used for motion analysis. The Rehabilitation Faculty Clinic is located on the ground floor of the SAHP at LSUHS and is where the anthropometric data will be collected. Our study has less than minimal risk. The PI will complete the DOA, including the assigning of roles and responsibilities, and educate each investigator at the time of signing.

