## **23.0 Local Number of Subjects**

- 23.1 At least 35 participants will be recruited locally.
- 23.2 We hope to enroll 35 participants.

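### The 20% attrition allowance is miscalculated: 35 enrolled leaves 28 completers, one fewer than the 29 the plan requires

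*Combined protocol and SAP*

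**What the plan says.** The sample-size argument is in section 11.2 and has three steps.

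- **Number needed:** "An N of 29 was calculated to achieve significant results". The effect size is d = .56, converted from r = .27. The error rates are given as "with beta = .80 and alpha = .05", two-tailed; the .80 is evidently power.
- **Attrition:** the authors "assumed an attrition rate of 20% given the repeated-measures design of the investigation".
- **Number to recruit:** "Therefore, a final N of 35 will be recruited for the successful completion of this study".

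No inflation formula is written out. The 35 is then used elsewhere:

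- Sections 9.2 and 22.1 treat 35 as the required number. The second student cohort is approached only if the first does not supply it, and recruitment continues only until it is reached.
- Section 20.2 sets it against a pool of 67 students: "Given the required N=35, there are enough potential participants to successfully complete this investigation".
- Section 23.1 words it as a floor, "At least 35 participants will be recruited locally", but section 23.2 gives 35 as the hoped-for enrolment.

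Section 11.1 names the test for the forward step-down test (FSDT): "Therefore, a Wilcoxon signed-rank test will be performed". For sEMG it plans a paired t-test, or the Wilcoxon test if assumptions fail.

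**The concern.** An attrition rate is the fraction of enrolled participants who do not finish. To end with a given number of completers, that number is divided by one minus the rate. Multiplying by one plus the rate gives too small an answer, and 35 is exactly what multiplication produces.

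Completers are the right unit here. The planned analyses are paired pre/post comparisons, so a participant without the follow-up visit contributes no pair, and the plan describes no imputation.

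What is at stake is whether the justification holds together. If attrition is as the plan assumes, the study should expect to finish below its own required number, having stopped recruiting at a figure presented as sufficient.

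**Working it through.** **Inputs, all from section 11.2:** 29 participants needed; attrition 20%; 35 to be recruited; d = .56 from r = .27; two-sided alpha .05; power .80. The Wilcoxon test for the FSDT is from section 11.1.

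**1. Reproducing the 29.** The conversion d = 2r / √(1 − r²) gives 2 × 0.27 / √(1 − 0.0729) = 0.561, matching .56. Power was taken from the noncentral t distribution for a paired test. For the Wilcoxon test, n was scaled by its asymptotic relative efficiency for normal differences, 3/π. The smallest n reaching 80% power at d = .56, two-sided, is:

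| Test | n |
|---|---|
| Wilcoxon, normal differences (3/π) | 29 |
| Paired t | 28 |
| Wilcoxon, minimum efficiency (0.864) | 32 |

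The plan's 29 is reproduced exactly as a two-sided Wilcoxon calculation.

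**2. Reproducing the 35.** 29 × (1 + 0.20) = 34.8, rounded up to 35. This matches the plan exactly.

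**3. The allowance as worded.** 29 / (1 − 0.20) = 36.25, rounded up to 37.

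| Enrolled | Expected completers at 20% loss | Reaches 29? |
|---|---|---|
| 35 | 35 × 0.80 = 28.0 | No |
| 36 | 36 × 0.80 = 28.8 | No |
| 37 | 37 × 0.80 = 29.6 | Yes |

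**4. What 35 can absorb.** 35 − 29 = 6 losses, and 6 / 35 = 17.1%. A 20% loss from 35 is 7.

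**5. Effect on power at d = .56.**

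| Completers | Wilcoxon (3/π) | Wilcoxon (0.864) | Paired t |
|---|---|---|---|
| 28 | 79.6% | 75.1% | 81.5% |
| 29 | 81.0% | 76.7% | 82.9% |

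A simulation of the Wilcoxon test with normal differences (20,000 runs) gave 79.1% at 28 and 81.2% at 29, in line with the 3/π column.

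**6. Chance of reaching 29.** As an illustration, assume each participant completes independently with probability 0.8. The binomial probability of at least 29 completers is 43% with 35 enrolled and 69% with 37.

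**The case against.** The strongest objection is that this hardly matters. The shortfall is one completer and about 1.4 percentage points of power. The 20% is a planning assumption with little stated basis, and no endpoint or analysis changes. All of that is true, and it limits the weight of the point. It does not make the three figures consistent.

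Second, section 11.2 does not name the test behind its 29. It says only "alpha = .05 for a two-tailed hypothesis from a repeated-measures design within groups analysis". With a paired t-test, 28 completers would still give 81.5% power. So the dip below 80% applies to the Wilcoxon test, which is the test planned for the FSDT and the one that reproduces 29. The shortfall against the plan's own 29 does not depend on this.

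Third, 79.6% assumes normally distributed differences, while section 11.1 calls the FSDT ordinal. This caution is fair: the figure should be quoted only with its basis. It is nevertheless the same basis on which 29 is reproduced.

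Fourth, the factor 1.2 is inferred, because the plan shows no formula. That is correct, but the contradiction needs only 35 × 0.80 = 28, whatever route led to 35.

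Fifth, the wording in section 23.1 would permit more than 35, and the pool of 67 leaves room. But sections 9.2 and 22.1 treat the requirement as met at 35, and section 23.2 gives the same figure, so the floor does not cure the problem.

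**Conclusion.** The concern holds. On the plan's own figures, 35 enrolled with 20% attrition yields 28 completers against a requirement of 29. The number consistent with both stated inputs is 37; the attrition consistent with 35 is about 17%.

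The arithmetic assumes only that attrition is a share of those enrolled and that an incomplete participant gives no pair for analysis. The power figures also take d = .56 as given and, for 79.6% and 81.0%, assume normal differences.

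This is a small error in a stated figure and does not seriously weaken the study. It should be corrected because the required number is wrong as justified, governs when recruitment stops, and is repeated across the protocol.

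**What to change.** Revise section 11.2 so that the three figures agree, in one of these ways:

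- **Keep 29 and 20%:** recruit 37. This is the only option that leaves both stated inputs unchanged. It needs two more participants from the 67 students in section 20.2. At the 220 minutes each in section 7.1, that is 2 × 220 = 440 participant-minutes.
- **Keep 35 and 29:** state that 35 allows for about 17% attrition (6 losses). This needs no extra participants, but the authors should say why 17% is a reasonable expectation and not simply the figure that fits.
- **Keep 35 and 20%:** state that 28 completers are expected, with Wilcoxon power just under 80% (79.6% at d = .56, on the normal-differences approximation). This also needs no extra participants.

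Whichever is chosen, section 11.2 should show the inflation formula and name the test used for the power calculation. The same edit can relabel the .80 as power, since beta would be .20. If the recruitment number changes, carry it through sections 9.2, 20.2, 22.1, 23.1 and 23.2. If 35 is kept, check that those sections still read correctly beside the revised 11.2. The cost is a sentence or two in 11.2 and, at most, one number changed in the other sections.

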11.3 See 9.4

11.4 The student investigators (CH and MS) will be educated on the proper procedures of the FSDT, sEMG data collection, and the HEP by the primary investigator (DF) and co-investigator (EM). The FSDT will be analyzed and scored by the two student investigators (CH and MS). The student investigators (CH and MS) will record and average their scores following the completion of five repetitions to improve the quality of the data. The sEMG electrodes will be placed on the female participants by EM and on the male participants by DF. CH will provide the pressure for the MVIC and explain the FSDT procedure to every participant. MS will explain the HEP and the compliance chart to the participants. The primary investigator (DF) is a board-certified orthopedic physical therapist with 10 years of experience, who has published research on this test. The co-investigator (EM) is also a board-certified orthopedic physical therapist with 5 years of experience, who also published research on this test with the primary investigator.

11.5 The data that will be collected during the entire study includes: participant number, height, weight, BMI, sex, leg dominance, FSDT pre and post HEP, recorded FSDT video, sEMG from gluteus medius and maximus on the dominant leg during FSDT pre and post HEP, and compliance. Data storage will follow the guidelines in section 9.4. The data will be stored for the duration of the study and throughout the following semester while analyzing and finalizing data for presentation. The data will be kept up to one year after the completion of the data analysis in event that the research wants to be continued. The only people to have access to this information will be the primary investigators, student investigators, and the co-investigator (DF, EM, CH, MS). All investigators are responsible for the receipt and transmission of the data. Data will be manually transported to DF office room 2-234 in the SAHP at LSUHS. Electronic data will remain on Sharepoint.

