Weakness of the hip abductors, external rotators, and extensors has been shown to lead to increased frontal and transverse plane motions at the hip. There is evidence to suggest that there are improvements in pain and overall function after a hip abductor and external rotation strengthening program. However, strength training has been unable to generate movement changes in women with PFP. In a case report on two separate patients with patellofemoral pain, muscle recruitment exercises, endurance training exercises, and core stability exercises were used to treat their pain, function, strength, gait, and biomechanical abnormalities. A combination of hip muscle activation and strengthening decreased the symptoms in these patients and improved their overall function, including stair navigation. In other areas of the body, activation training vs strength training has been compared to see what yields better outcomes. There is a current hole in the literature regarding whether activation

training alone of the hip musculature can alter frontal plane movements of the lower extremity. There is evidence to support that activation training of certain muscles may lead to better performances of the muscle during more advanced training programs. Increasing core activation during exercises focused on the hip musculature, such as clam shells, side-lying hip abduction, and prone hip extension, was shown to overall increase muscle activation of the LE. As for dosing of these exercises, one minute isometric holds have been shown to improve recruitment of the hip muscles during weight bearing activities. Hip muscle activation training is an area of treatment which needs more research to see the overall benefits, but it has been explored in core musculature, so we hope to examine if similar results will occur at the hip joint.

- 2.2 Our participants will execute the hip activation intervention via an 8 week home exercise program (HEP). This is the first study on this topic by the authors; however, two of the authors have previously published work using the FSDT as an outcome measure, using the same procedures for assessment as in this investigation. The study will evaluate the effects of a hip activation training program via HEP on the FSDT, as well as compliance measures of the HEP to analyze a dose-response predictive relationship.

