## **9.0 Procedures Involved\***

- 9.1 The study will utilize a repeated-measures design, where all participants will perform the FSDT for assessment pre- and post-intervention via an HEP while sEMG data is being collected from the gluteus medius and gluteus maximus. All of the activities listed above will be performed on the dominant LE. The HEP will be a combination of hip musculature activation exercises used by previous researchers that show an increase in hip muscle recruitment. Core activation via a side plank will be added to the clam exercise and the side-lying hip abduction exercise. In this design the dependent variables are the scores on the FSDT pre- and post-HEP, sEMG pre-and post-HEP, and compliance with the HEP. The independent variable is the performance of the eight-week HEP. Two physical therapist students will perform the FSDT assessments and sEMG data collection (CH and MS). Two faculty members will also assist with data collection (DF and EM). Prior to data collection and assessments, the two students (CH and MS) will be educated by the primary investigator (DF), who is a board-certified orthopedic clinical specialist physical therapist with ten years of experience, on the FSDT protocol. Scoring guidelines of the FSDT will be reviewed according to the study by Park *et al* and practiced prior to data collection. The sEMG electrode placement will come from *The ABC of EMG*. The procedure for collection of the maximum volitional isometric contraction (MVIC) of the gluteus medius will follow the protocol used in a study by Harput *et al*. The MVIC of the gluteus maximus will follow the protocol used in a study by Selkowitz *et al*, with the knee flexed to 90° in prone. The same methodology will be used from [name] and [name] for scoring and reporting of the FSDT scores.

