**12.0 Provisions to Monitor the Data to Ensure the Safety of Subjects\***

12.1 N/A

**13.0 Withdrawal of Subjects\***

13.1 Non-study related injury that affects ability to complete HEP or FSDT post intervention.

13.2 After the participant has notified any investigator that they wish no longer to continue or no longer meet the inclusion/exclusion criteria, the investigators will notify the participant that they have been

withdrawn from the study and document the nature for withdrawal and date. The participant will return the compliance sheet to the investigators.

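### The Aim 1 outcome is rated by two students who also help run the sessions; the protocol states no masking to visit and gives the planned FSDT video no role in scoring.

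*Combined protocol and SAP*

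**What the plan says.** Section 11.4 names the raters: "The FSDT will be analyzed and scored by the two student investigators". They "will record and average their scores following the completion of five repetitions". Section 9.2 also has both students score and average, and has the follow-up visit repeat the baseline procedures. Sections 9.2 and 11.4 give the same students other tasks. One resists the maximal contractions and instructs every participant in the FSDT. The other teaches the HEP and the compliance chart, and at the first visit this follows the baseline FSDT.

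Section 9.1 takes over the method of a published pilot study by two of the authors (reference 12) "for scoring and reporting of the FSDT scores", and section 2.2 describes that work as "using the same procedures for assessment as in this investigation".

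Sections 9.5 and 11.5 list recorded FSDT video among the data, and 9.5 has it collected both before and after the intervention. No section says who views it, when, or whether any score comes from it. Masking of raters is not mentioned anywhere. Participant numbers (9.2, 9.4, 24.1) and the room divider (24.2) are described as confidentiality measures.

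**The concern.** The FSDT score is a judgement, and section 11.1 treats it as ordinal. A rater at the session would know whether it was the first visit or the follow-up, because the HEP is taught at one and the compliance sheet is returned at the other.

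In a randomised comparison, a leniency applied equally to both arms would largely cancel. Here everyone receives the HEP and Aim 1 rests on a single pre/post contrast, so a leniency at follow-up that both raters share cannot be told apart from an effect of the program. The stated safeguards (guideline review, scoring practice and averaging two raters) improve consistency and reduce independent error, but none acts on an expectation held by both raters. The surface EMG is instrument-based, but it answers Aim 2 and cannot correct the FSDT.

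Compliance is a side point. The sheet is returned at the follow-up visit (9.2), and section 11.5 says: "All investigators are responsible for the receipt and transmission of the data". A rater could therefore see it before scoring, although the order and the recipient are not stated.

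**Working it through.** **What the text settles.**

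| Question | Where | Answer in the text |
|---|---|---|
| Who scores | 9.2, 11.4 | The two students only |
| Contact with participants | 9.2, 11.4 | One explains the test; the other teaches the HEP |
| Live or video | 9.2, 11.4 | Not stated |
| Masked to visit | none | Not stated in the protocol text |
| Use of the video | 9.5, 11.5 | Listed as data, no use given |
| Adopted method | 9.1, 2.2 | By reference; content not visible here |
| Comparison group | 9.1 | None described |

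**Why averaging does not help.** Write rater j's score at follow-up as true score + b + e_j, with b shared and e_j independent. The mean of two raters is true score + b + (e_1 + e_2)/2. The independent error variance is halved and b is unchanged. If b is zero at baseline, the whole of b enters the paired difference.

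**The plan's own figure.** Section 11.2 gives r = .27, d = .56, two-tailed alpha .05, power .80 (printed as beta) and N = 29.
- d = 2r/√(1 − r²) = 0.54/√0.9271 = 0.561.
- Reading d as paired-difference SD units, with signed-rank efficiency 3/π and a noncentral t: n = 28 gives effective n 28 × 3/π = 26.74 and power .796; n = 29 gives 27.69 and power .810. N = 29 reproduces.
- Completers after the assumed attrition: 35 × 0.80 = 28. Without attrition: 35.

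**Illustration of size.** Assume no true change and a shared shift b in SD of the paired difference. The documents give no value for b. The plan's d serves only as a yardstick: 0.56/4 = 0.14 and 0.56/2 = 0.28. Noncentrality is b × √(n × 3/π), tested two-sided at .05.

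| n | Effective n | b | Noncentrality | Chance of a significant result |
|---|---|---|---|---|
| 28 | 26.74 | 0 | 0 | .050 |
| 28 | 26.74 | 0.14 | 0.724 | .107 |
| 28 | 26.74 | 0.28 | 1.448 | .286 |
| 35 | 33.42 | 0.14 | 0.809 | .123 |
| 35 | 33.42 | 0.28 | 1.619 | .349 |

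Coarse scoring lowers these figures. A simulated signed-rank test at n = 28 (10,000 runs, zero differences dropped, differences rounded to steps of 2 SD) gave .080 and .207. That case makes about two-thirds of pairs tie at zero and is deliberately extreme; the documents give no FSDT score range or SD. Together the ranges are about 8 to 12% for 0.14 SD and 21 to 35% for 0.28 SD.

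**Compliance.** Section 11.1 names no dose-response test, so a Spearman correlation is assumed. A uniform 0.28 SD shift with no true relation, n = 28, left the rejection rate at .050. Only scoring that varied with the compliance seen could create a relationship.

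**The case against.** The strongest reply is that the scoring method is not left open. Sections 2.2 and 9.1 adopt it by reference, and reference 12 is attached to the scoring sentences in 9.2 and 11.4. If that method scores from coded video, only a sentence is missing. This stands, and it is why the fix is conditional.

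Second, live scoring is only inferred. The words on completing five repetitions may define the scoring unit, since 9.2 gives one score per set of five, and the phrase about analysing and scoring could include video review. This also stands. A reader might infer that the raters will certainly score live and unmasked; the documents do not say so. They leave it unstated how the Aim 1 score is produced.

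Third, the benefit of masked video is limited. The raters would be watching fellow students and may remember sessions. This stands in part: identity stays visible, but a pre/post contrast mainly needs the visit concealed, and coded, shuffled clips can do much of that.

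Fourth, the shift sizes are invented. They are, and the recommendation does not rest on them.

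**Conclusion.** The point holds in a limited form. The protocol leaves the only Aim 1 contrast open to an expectation shared by its two raters, states no masking to visit, and gives no role to the video that could provide it. The size is unknown. The range of 8 to 12% (0.14 SD) and 21 to 35% (0.28 SD) false positives assumes no true change, a shift with no source in the documents, and 28 to 35 pairs.

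Two stronger readings go too far. A reader might conclude that the Aim 1 result will be biased; nothing in the documents shows that a shift exists, and the adopted method may already prevent one. A reader might also conclude that Aim 3 is compromised; a uniform shift creates no compliance relationship, and nothing shows that a rater reads the sheet before scoring. Compliance therefore stays a minor point.

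**What to change.** State in 9.2 and 11.4 whether the FSDT is scored live or from video, and whether the method adopted in 9.1 masks raters. If it does, say so; nothing more is needed.

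If it does not, take the analysed FSDT score from the pre and post videos already planned. A faculty investigator codes the clips and shuffles them across visits. The same two students score them after follow-up is complete, without visit or compliance information, and the scores are averaged as planned. Adjust the reference in 9.1 where the procedure differs, and the timeline wording in 8.1 and 20.2, because data collection is due to end by May 2023 and scoring would fall later. Report that masking covers visit, not identity.

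If usable video cannot be obtained, state that scoring is live and unmasked, and limit the Aim 1 conclusion accordingly.

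Cost: 28 × 2 = 56 clips, at most 35 × 2 = 70, so 112 to 140 ratings across two raters. No visits or staff are added. Under 20.2, in summer 2023 "the student investigators will begin analyzing the data and disseminating", and 20.1 has faculty helping as needed, "including assisting with data collection and analysis", although 20.2 budgets each at only 5% FTE. The downsides are dependence on a camera view the plan does not describe, possible departure from the method that supplied the effect size in 11.2, and participants who remain recognisable. Test familiarity and other single-group pre/post effects would remain.
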